## 9.2 Laboratory Studies Performed

Flow cytometry will be used to evaluate leukocyte subpopulations (e.g., CD3, CD4, CD45, TCRγδ, CD14, CD16, CD56). Additional surface markers will be used to discriminate different maturation stages of effector cells (CD28, CD27, CD45RA, CD3, CD8, CCR7, CD4, CD45): naive T cells, central memory, effector memory and CD45RA expressing effector memory cells; Tregs (CD4+CD25+FoxP3+CD127low); Th17 (IL-17positive). To assess activation levels of circulating T-cells, a panel of activation markers will be used (e.g., CD38, CD25, CD69, HLA-DR). The immunology panel may be expanded to include other markers. Plasma cytokine levels will be measured by ELISA.

## 10.0 STUDY CALENDAR

All assessments may increase in frequency as clinically indicated.

Treatment or Assessment ( $\pm$ 7 days) a	Screening b	Cycle 1				C2-3	C4	C5-6	C7	C8-12	C13 & every 3 Cycles c	EoT d	Follow-up e
		D1	D8	D15	D22	D1	D1	D1	D1	D1			
Informed consent	X												
Medical history g	X	X											
Inclusion/Exclusion Criteria h	X												
Registration i	X												
Other anti-cancer treatment j	X												
Concurrent med review	X	X	X	X	X	X	X	X	X	X	X		X
Physical exam l	X	X	X	X	X	X	X	X	X	X	X		X
Vital signs m	X	X	X	X	X	X	X	X	X	X	X		X
ECOG Performance Status ( Appendix A )	X	X	X	X	X	X	X	X	X	X	X		X
Adverse Event Eval n										X			
12-lead EKG o	X												
Pregnancy test p	X	X										X	
Hematology q	X	X	X	X	X	X	X	X	X	X	X	X	X
Biochemistry r	X	X	X	X	X	X	X	X	X	X	X	X	X
Serum Immunoglobulins s	X										X		
Hemolysis parameters t	X	X	X	X	X	X	X	X	X	X	X	X	X
PT, aPTT, INR	X												
HBsAg, HBcAb, HCVAb, RPR	X												
HIV test	X												
CT Imaging and CLL assessment ( Appendix C ) u	X								X		X		
Bone Marrow Biopsy v											X		
AIHA disease assessment ( Appendix B )	X					X		X		X	X		X

Molecular and Genetic Tests W	X													
Acalabrutinib X		Orally, every 12 hours												
Medication diary Y		X	X	X	X	X	X	X	X	X	X			
Research blood collection Z	X					X		X		X		X		

a. Ideally the clinic visit and all the study requirements should be performed on Day 1 of each cycle as indicated, but may be performed within 7 days before or after the scheduled day. Each treatment cycle is 28 days
 
b. Screening activities to occur within 30 days prior to the start of protocol therapy.
 
c. Protocol therapy may last up to 12 cycles, until unacceptable toxicity or disease progression (see Section 5.6 for more comprehensive list). At the end of 12 cycles, treatment with acalabrutinib may be continued if the study participant might benefit from the ongoing therapy in the opinion of the treating physician.
 
d. An End of Treatment (EOT) visit is required for safety assessments for any subjects who permanently discontinue study drug for any reason, including disease progression. This visit should occur at 30 (<math>\pm 7</math>) days from time of the last dose of study drug to monitor for resolution or progression of AEs and to document the occurrence of any new events, regardless of whether the subject receives a new CLL therapy or demonstrates disease progression within this timeframe. Subjects who withdraw consent for study treatment should still be encouraged to complete the EOT assessments, but these assessments cannot be mandated if subject consent for further study participation is withdrawn.
 
e. Follow-up assessments are to occur in accordance with standard of care, with participants visits occurring at least every 4 months, up to 12 months from time last dose of study drug.
 
f. Informed consent process to be fully documented (see Section 17.4). Informed consent must occur prior to any research only (non-SOC) screening procedures.
 
g. A medical history will be obtained by the investigator or qualified designee. To include information on demographics, all active conditions, and any condition diagnosed within the prior 10 years that are considered to be clinically significant by the Investigator. Details regarding the participant's cancer will be recorded separately and not listed as medical history.
 
h. Eligibility criteria are detailed in Section 3.0.
 
i. Registration into a COH clinical trial management system (CTMS)
 
j. Document the following disease-specific information: number of prior treatment regimens for CLL and AIHA; drugs previously used in the therapy of CLL and AIHA; including (if available): therapy dates, and response, concomitant autoimmune disorders, including hematologic (immune thrombocytopenia, immune-mediated neutropenia) and non-hematologic (e.g., rheumatoid arthritis and other rheumatologic conditions; inflammatory bowel disease [Crohn's disease, ulcerative colitis]), History of ibrutinib intolerance (present versus not), Rai stage at diagnosis (if known) and the time of study entry.
 
k. Current list of medications will be acquired concurrent with medical history. See Section 5.9 for concomitant medication restrictions and guidelines. Baseline transfusion requirements must be assessed prior to start of study drug. Transfusion requirements prior to study start up to 6 months will be collected/documents, if available. Transfusion requirement will be assessed on day 1 of each cycle and number of units of PRBCs and platelets transfused during the previous cycle will be documented. Enter new medications started during the trial through the end of treatment visit. Record all medications taken for grade 3 and 4 SAEs.
 
l. Physical examination must be performed by a medically qualified individual such as a licensed physician, Physician's Assistant or advanced Registered Nurse Practitioner as local law permits. Baseline complete physical exam per institutional standards and may include evaluating: weight, general appearance, head, ears, eyes, nose, throat, neck, skin, cardiovascular system, respiratory system, gastrointestinal system, and nervous system. Height is only required as part of screening. Weight should be recorded at each visit. More extensive physical exams will be performed if guided by the development of new symptoms.
 
m. Vital signs: blood pressure, heart rate, temperature, and oxygen saturation by pulse oximetry.
														

- n. Adverse events will be assessed using the [CTCAE v5.0](#) (non-hematologic) and IWCLL 2018 (hematologic). SAEs related to study procedures will be recorded and reported from the time the participant signs the Consent Form. Please see Section 14 for routine AE assessing and reporting ([Section 14.6](#)) and SAE reporting ([Section 14.7](#)).
- o. Electrocardiogram (ECG): resting 12-lead ECGs will be recorded at screening, and as clinically indicated throughout the study.
- p. A serum or urine pregnancy test is required during screening for women of childbearing potential. If urine pregnancy results cannot be confirmed as negative, a serum pregnancy test is required. For Day 1 Cycle 1, a pregnancy test may be omitted if previously obtained within 72 hours prior to first dose of trial treatment. Pregnancy tests (serum and/or urine tests) should be repeated, if required, per institutional guidelines. A serum or urine pregnancy test will be done for women of childbearing potential any time for missed or late menses, and at the end of treatment. If the urine pregnancy test is positive, a serum pregnancy test must be performed per institutional standards.
- q. Hematology: Hemoglobin; hematocrit; mean corpuscular volume (MCV); reticulocyte count (absolute and relative); leukocyte count; differential count; platelets. Additional hematology may be performed thereafter as clinically indicated
- r. Biochemistry: Comprehensive metabolic panel (CMP), including: Na, K, Cl, CO2, BUN, Creatinine, Ca, glucose, Albumin, Alkaline Phosphatase, total bilirubin, AST, ALT, total protein.
- s. Serum immunoglobulins, IgG, IgM, and IgA are required at screening and on cycle 13 D1.
- t. Hemolysis parameters: Reticulocytes, lactate dehydrogenase (LDH), bilirubin (direct/indirect), haptoglobin and DAT.
- u. Computed tomography (CT) scan of neck, chest, abdomen and pelvis per institutional guidelines (with intravenous contrast, wherever possible) will be performed for response assessment at screening, C7D1, C13D1 and annually thereafter. CLL response will be evaluated every time imaging is performed. A bone marrow biopsy will be performed only if CR is suspected. Positron emission tomography with CT (PET-CT) and/or magnetic resonance imaging studies may be performed as clinically indicated, per institutional guidelines, and is acceptable in place of CT, if performed.
- v. Bone Marrow Biopsy - A bone marrow biopsy will be performed to document CR within 90 days of the imaging test where CR was suspected. - A bone marrow biopsy may be performed at screening per investigator discretion, but is not required.
- w. Molecular and Genetic Assays: testing results are not required to proceed with study enrollment. Cellular and molecular assays will be performed according to institutional standards, at screening on specimens obtained within 6 months if no intervening therapy. The following assays will be planned as per standard of care: CLL FISH Panel (as per institutional standards), immunoglobulin heavy chain (IGHV) mutational status (unless already known), prognostic gene panel (e.g., HopeSeq panel performed at COH).
- x. Participants will self-administer oral study agent, acalabrutinib. Participants will receive instruction on how to administer study drug from a physician, clinical research nurse, or other designated, qualified healthcare provider
- y. Assessment of study agent adherence. Participants will be provided with a medical diary (Appendix D) and are required to record the date, dose, and the time of the ingestion. This will be reviewed at each clinic visit to assess compliance.
- z. Research blood may be collected as part of any planned blood draw that is performed per institutional standard.

## 11.0 ENDPOINT DEFINITIONS/MEASUREMENT OF EFFECT

### 11.1 Primary Endpoint(s)

Objective	Endpoint	Start	End
Assess the efficacy of acalabrutinib in CLL patients with relapsed or refractory AIHA	AIHA ORR after 6 cycles [ORR defined as proportion of patients who achieve complete and partial response; refer to Appendix B ]	First dose of study drug [i.e. C1 Day 1]	After 6 cycles of therapy

Primary endpoint of AIHA ORR after 6 cycles will be defined as the proportion of patients achieving AIHA complete or partial response after 6 cycles. Patients evaluable for this endpoint include: 1) those who receive at least 6 cycles of treatment and have AIHA response evaluation after 6 cycles (each cycle = 28 days); 2) patients who terminate acalabrutinib prior to completing 6 cycles due to AIHA or CLL progressive disease (they will be counted as non-responders).

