#### 4.3 Screen Failures and Registered Participants Who Do Not begin Study Treatment

Notify the DCC immediately if the participant screen fails after registration or if the participant does not start treatment.

For non-COH sites, the reason for screen failure will be documented in the registration coversheet ([Appendix E](#)) and submitted to the DCC.

Issues that would cause treatment delays should be discussed with the Study Principal Investigator.

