## 5.6 Duration of Therapy and Criteria for Removal from Protocol Therapy

Participants will receive protocol therapy until one of the below criteria are met:

- Completed protocol therapy (see [Section 5.3](#))
- AIHA relapse or progressive disease for CLL
- Participant is deemed intolerant to protocol therapy because of toxicity, despite dose modification/delay
- General or specific changes in the patient's condition which render the patient unacceptable for further treatment in the judgment of the investigator
- Withdrawal of consent for further protocol therapy (See [Section 17.5](#))

Once participants meet criteria for removal from protocol therapy, the participant should then proceed to End of Treatment assessments, and then to follow-up (Refer to the Follow-Up section below).

Documentation of the reason for discontinuing protocol therapy and the date effective should be made in the Electronic Health Record/medical record and appropriate eCRF.

The COH DCC and the Study PI should be promptly notified of the change in participant status.

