### 12.2 Sample Size and Power

For warm AIHA, initial treatment with prednisone is associated with responses in 70%-85% of patients; however, even this is short-lived as only 15% to 20% of patients achieve long-term remission upon withdrawal of corticosteroids. Subsequent lines of immunosuppressive therapy (e.g., cyclophosphamide, rituximab) carry initial response rates from 40-60%, but durable responses occur in only 20% to 30% treated patients.

A sample size of 20 achieves an approximate 87% power using a one-sided binomial exact test with a significance level (alpha) of 0.05 for detecting improvement of 0.3 (0.6 from 0.3) in response rate, based upon the assumption that a response of 30% or less indicates no benefit. The actual type I error is 0.048 and the exact binomial test will require 10 or more responders in 20 patients evaluable for the primary endpoint to reject the null hypothesis of 0.3. Anticipating up to 10% patients not evaluable for the primary endpoint, a total of 22 participants will be enrolled.

Study enrollment is anticipated to occur over 36 months at a rate of approximately 7 patients per year

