#### 12.2.1 Analysis Populations

The evaluable patients for the clinical endpoints will be eligible participants who received at least 1 dose of protocol treatment, unless otherwise specified in Section 11.1 under the specific/particular endpoint.

The evaluable patients for the exploratory endpoints will be eligible participants who received at least 1 dose of protocol treatment and has at least 1 correlative blood specimen collected on the study.

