### 12.3 Study Stopping Rules

The overall study will be paused if any of the following occurs:

- ≥2 of the first six participants develop any grade 4 toxicity (assessed as possibly, probably, or definitely related to study drug) during cycle 1 of treatment, or
- ≥3 of the first 6 participants need to discontinue therapy with acalabrutinib during cycle 1 of treatment due to perceived lack of efficacy, or
- Death with possible or higher attribution to acalabrutinib.

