## 12.5 Handling of Missing Data

Every attempt will be made to obtain data at the defined time points as described in the primary and secondary endpoints. If the data are not sufficient to analyze specific endpoints, the participant's data may be excluded entirely or partially, depending on the specific endpoints in question. No missing data will be imputed. Whenever possible, all available data will be included in the analysis. A sample size for each analysis will be clearly stated along with the reason for exclusion, if any participant is excluded from the analysis due to missing data.

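### Section 11.1 drops treated patients who stop before 6 cycles for toxicity, death without progression or withdrawal from the primary response rate, and leaves lack-of-efficacy stops unassigned

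*Combined protocol and SAP*

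**What the plan says.** Section 11.1 defines the primary endpoint as the proportion with AIHA complete or partial response after 6 cycles. It then names the evaluable patients: those who received at least 6 cycles and had an AIHA evaluation afterwards, and "patients who terminate acalabrutinib prior to completing 6 cycles due to AIHA or CLL progressive disease (they will be counted as non-responders").

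Other sections bear on the same denominator:

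- Section 12.2.1 sets the default population as "eligible participants who received at least 1 dose of protocol treatment, unless otherwise specified in Section 11.1". Section 11.1 does specify otherwise, so the default gives way.
- Section 12.2 sizes the test for 20 evaluable patients and adds: "Anticipating up to 10% patients not evaluable for the primary endpoint, a total of 22 participants will be enrolled". It describes the null as "based upon the assumption that a response of 30% or less indicates no benefit".
- Section 12.5 imputes nothing and permits exclusion, on condition that "A sample size for each analysis will be clearly stated along with the reason for exclusion".
- Section 5.6 lists reasons for leaving treatment that 11.1 does not mention, including "Participant is deemed intolerant to protocol therapy because of toxicity, despite dose modification/delay" and withdrawal of consent.
- Section 12.3 has a pause rule that counts participants who "need to discontinue therapy with acalabrutinib during cycle 1 of treatment due to perceived lack of efficacy".
- Section 4.3 covers registered patients who never start, asking sites to notify the coordinating center "if the participant screen fails after registration or if the participant does not start treatment".
- Appendix B defines AIHA complete and partial response only. Section 11.2 gives a minimum for AIHA relapse. AIHA progressive disease is defined nowhere.

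**The concern.** The exclusion depends on what happened after treatment began, and it works in one direction. A patient who stops in cycle 3 for toxicity has no documented response after cycle 6. Removing that patient shrinks the denominator and leaves the numerator unchanged.

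The list in 11.1 could be read as open-ended, since it says which patients the evaluable set includes. Section 12.2 argues against that reading, because its allowance for non-evaluable patients means that some are expected to fall outside. If the list were open-ended, the denominator would be undefined, which also needs repair.

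Lack-of-efficacy stops add a second problem. Section 12.3 expects them, yet 11.1 keeps as failures only stops for progression. A patient who never responded and stops could be recorded as progressing (a failure) or under another reason (excluded). The trial is open-label and response is investigator-assessed, so the recorded reason for stopping can decide whether the patient counts.

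At stake are the reported response rate and, near the cut-off, the conclusion of the trial. The 3- and 12-cycle AIHA response rates have the same gap. The CLL response rates keep as failures only early stops for CLL progression.

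**Working it through.** **Inputs (Section 12.2):** exact binomial test, one-sided alpha 0.05, null 0.30, alternative 0.60, 20 evaluable, success at 10 or more responders, up to 10% not evaluable, 22 enrolled. The documents give no rate of early stopping, so ranges below are assumptions.

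**1. The plan's own figures.** With X ~ Bin(20, p):

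- P(X ≥ 10 | 0.30) = 0.0480, against the stated 0.048.
- P(X ≥ 10 | 0.60) = 0.8725, against the stated 87%.
- A cut-off of 9 would give 0.113, so 10 is the smallest valid cut-off.

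The design reproduces.

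**2. Exact cut-off by denominator**

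| n | Cut-off | Alpha at 0.30 | Power at 0.60 | P(X ≥ 10) at 0.30 |
|---|---|---|---|---|
| 20 | 10 | 0.0480 | 0.8725 | 0.0480 |
| 21 | 11 | 0.0264 | 0.8256 | 0.0676 |
| 22 | 11 | 0.0387 | 0.8793 | 0.0916 |

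**3. Same data, two denominators, 10 responders**

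- 22 treated, 2 dropped: 10/20 = 50.0% (95% Clopper-Pearson 27.2 to 72.8), p = 0.048, reject. On all treated, 10/22 = 45.5% (24.4 to 67.8), p = 0.092, do not reject.
- 21 treated, 1 dropped: 10/20, p = 0.048, against 10/21, p = 0.068. The decision flips.
- 22 treated, 1 dropped: the cut-off is 11 for both 21 and 22, so no flip is possible.
- Non-evaluable patients never dosed: both denominators are the same, so no flip.

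**4. How often the two sets disagree.** Take 22 treated, number dropped D ~ Bin(22, d), and responders X ~ Bin(22 − D, q), where q is the response rate among evaluable patients. Disagreement means that X reaches the exact cut-off for 22 − D but is below 11.

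| Dropped, d | q = 0.3 | q = 0.4 | q = 0.5 | q = 0.6 | q = 0.7 |
|---|---|---|---|---|---|
| 5% | 0.008 | 0.033 | 0.054 | 0.039 | 0.012 |
| 10% | 0.017 | 0.071 | 0.124 | 0.105 | 0.042 |

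**5. False-positive rate, if the 30% null is an all-treated rate.** Use the same mixture and the exact cut-off for each n. If every excluded patient is a failure, q = 0.30/(1 − d). At d = 0.10, q = 0.30/0.90 = 0.333.

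| d | 2.5% | 5% | 7.5% | 10% |
|---|---|---|---|---|
| P(reject) | 0.042 | 0.050 | 0.059 | 0.069 |

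Three variations at d = 0.10 remove the inflation:

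- Half the excluded fail and the rest respond at 0.30: q = (0.30 − 0.10 × 0.5 × 0.30)/0.90 = 0.3167, P(reject) = 0.050.
- Exclusion unrelated to outcome: q = 0.30, P(reject) = 0.035.
- True all-treated rate 0.25, all excluded fail: q = 0.25/0.90 = 0.2778, P(reject) = 0.021.

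**6. Power with all 22 treated and a cut-off of 11**

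- 60% is the all-treated rate: 0.879.
- 60% is a completer rate and early exits count as failures: with 10% exits, 0.60 × 0.90 = 0.54 and power is 0.723. With 2 exits of 22, 0.60 × 20/22 = 0.5455 and power is 0.740.
- For comparison, the current rule under the mixture in step 4 (d = 0.10, q = 0.60) has power 0.828.

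**The case against.** The strongest reply is that the evaluable set is declared and coherent. Section 11.1 defines it, 12.2 sizes the test for it, and alpha is right for it. Response among all treated patients is a different estimand, and preferring it does not show an error in the plan's own terms. That stands as far as the alpha statement goes. It does not answer the one-directional exclusion of treated patients for reasons tied to how they fared on the drug.

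The excluded patients are also not invisible. Section 12.5 requires counts and reasons, every dosed patient is in the toxicity analysis, and AIHA relapse-free survival counts deaths. A reader could rebuild 10/22 from the report. This is disclosure after the event, however, and no all-treated response rate is planned.

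On lack of efficacy, the relapse minimum in 11.2 (hemoglobin below 10 g/dL with hemolysis) is close to the entry criterion in 3.1, so many persistent non-responders might be classed as failures anyway. That is plausible, but 11.1 speaks of progression, not relapse, and relapse ordinarily presupposes a response.

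On size, response rates of 40% to 60% lie around the cut-off. At 30% or 70% the disagreement is smaller (step 4). The 10% is a ceiling and may include patients never dosed. Both qualifications stand.

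On cost, if 60% is a completer rate with 10% exits, moving to all treated takes power from about 0.83 to about 0.72. That is a real price, and it is why the plan must say which rate the 60% is. An all-treated sensitivity analysis alone would avoid the price, but the outcome-related exclusion would remain in the test that decides the trial.

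**Conclusion.** The concern holds and should be fixed. That 11.1 leaves out dosed patients who stop early for toxicity, withdrawal or death without progression follows from the text and needs no assumption. So does the direction of the effect. With 10 responders the estimate moves by 4.5 percentage points (50.0% to 45.5%) when 2 of 22 treated patients are dropped, and the decision reverses. A reversal requires that the dropped patients were dosed and that the result is near the cut-off.

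The false-positive figures are weaker evidence. They exceed 0.05 only if 30% is read as an all-treated rate, nearly all excluded patients are failures, and more than about 5% are excluded. Section 12.2 calls the 30% an assumption and sets it beside a figure for durable response, so the all-treated reading is an inference. The case for change does not depend on it.

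**What to change.** - **Section 11.1:** make the primary set all eligible participants with at least one dose, which is already the default in 12.2.1. Count as a non-responder anyone without a documented AIHA complete or partial response at the assessment after cycle 6. This covers stops for toxicity, death, withdrawal and lack of efficacy, and patients who complete 6 cycles but miss the assessment.
- **Section 12.5:** state that this is part of the endpoint definition and not imputation.
- **Section 12.2:** give the exact cut-off for the number actually treated (11 of 22, 11 of 21, 10 of 20). State whether 60% is an all-treated or a completer rate, and restate the power.
- **Sensitivity analysis:** keep the current evaluable set in this role, with AIHA progressive disease defined by the sponsor.
- **Section 11.2:** use the same denominator for AIHA response at 3 and 12 cycles and for CLL response.

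The cost is wording in four sections, with no new data and no increase in enrolment. The reported response rate will be slightly lower, and a patient in response who stops before cycle 6 for toxicity will count as a non-responder. If 60% is the all-treated rate, power is 0.879 with 22 treated, 0.826 with 21 and 0.873 with 20. If it is a completer rate with about 10% early exits, power is about 0.72 to 0.74 with 22 treated.
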